12.2.2 Pharmacokinetics

Since the active major metabolites of RPC1063, CC112273 and CC1084037, have long elimination half-lives, a total of 3 PK blood samples per patient will be collected at the End of Treatment/Early Termination Visit and on Day 28 and Day 90 Safety Follow-up Visits to assess if ALC recovery after study drug discontinuation is related to plasma concentrations of these metabolites (see Table 2). The sampling will continue until the Sponsor determines enough data is obtained to achieve PK recovery modeling but may require up to approximately 80 evaluable subjects. If deemed necessary, the data obtained from these subjects may be combined with those from other clinical studies for pharmacometric analysis.

Additional PK samples may be obtained for patients with prolonged ALC recovery or for appropriate safety reasons (ie, AEs resulting in discontinuation, or relevant SAEs) at the request of and in consultation with the Medical Monitor.

12.3. Adverse and Serious Adverse Events

12.3.1 Definition of Adverse Events

An AE is any untoward medical occurrence in a patient or clinical investigation patient administered a pharmaceutical product, which does not necessarily have a causal relationship with this treatment. An AE can therefore be any unfavorable or unintended sign (including an abnormal laboratory finding), symptom, or disease temporally associated with the use of medicinal product, whether or not considered related to the investigational medicinal product (ICH E2A, II.A.1).

Relapses (confirmed or unconfirmed) and MS disease progression will be monitored as trial endpoints, but will not be recorded as AEs.

AEs will be monitored for each patient from their first dose following enrollment and throughout the duration of their participation in the trial, including the 90-Day Safety Follow-up Visit. Investigators will ask the patient at each visit if they have experienced any untoward occurrence since the last trial visit. All AEs will be recorded on the eCRFs provided: a description of the event, severity, time of occurrence, duration, any action (eg, treatment and follow up tests) and the outcome should be provided along with the Investigator's assessment of the relationship to the investigational drug.

In cases of surgical or diagnostic procedures, the condition/illness leading to such a procedure is considered as the AE rather than the procedure itself.

An Adverse Drug Reaction (ADR) is defined as all noxious and unintended responses to a medicinal product related to any dose (ICH E2A, II.A.2).

An Unexpected ADR is defined as an adverse reaction, the nature of which is not consistent with the applicable product information (ICH E2A, II.A.3).

Each AE is to be evaluated for duration, severity, seriousness and causal relationship to the investigational drug. The action taken and the outcome must also be recorded.

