Procedure	Baseline (Day 1)^a	Every 3/6 Months^p (± 10 days)	Every 12 Months (± 10 days)	Unscheduled Relapse Visit^b	End of Treatment/ Early Term^c	ALC Follow- up Visit^c (every 14 days after last dose ± 3 days)	Safety Follow- up Visit^q (28 days after last dose ± 7 days)	Safety Follow- up Visit^{m, q} (90 days after last dose ± 10 days)
Brain MRI ⁿ	X ⁱ		X		X			
EDSS and neurological examination	X ^a	X	X	X	X			
MSFC and LCLA	X ^a		X	X	X			
MSQOL-54	X ^a		X		X			
Pulmonary function tests ^j	X ^a		X		X			
OCT ^k	X ^a		X		X			
Dermatological (skin) examination	X ^a		X		X			
Columbia-Suicide Severity Rating Scale (C-SSRS)	X ^a	X	X	X	X		X	X
Prior/concomitant therapy	X	X	X	X	X		X	X
AEs/SAEs	X	X	X	X	X		X	X
PK Sampling					X ^o		X ^o	X ^o
Blood Sample ^r	A blood sample will be collected at the patient's next visit after this amendment is implemented, every 6 months thereafter, and at the end of treatment for potential measurements of immune response (eg, SARS-CoV-2 serology).							

Confidential and Proprietary

Footnotes are provided on the next page.

- ^a Perform specified procedures at Baseline (Day 1) only if they were not performed at the end of treatment/study visit of the parent trial or not within the timeframe prior to the end of treatment/study visit specified by the parent trial protocol. Perform a urine pregnancy test at Baseline if more than 1 month has elapsed from the last pregnancy test in the parent trial. Approval from the Sponsor's representative is required for enrollment more than 14 days after the patient's last dose of investigational drug in the parent trial, and the patient must undergo RPC1063 dose escalation. For patients from RPC01-1001, the RPC01-3001 informed consent process may begin on the last day of dosing in RPC01-1001. For the same patients, Baseline (Day 1) brain MRI, OCT, and pulmonary function tests are not required to occur on the same day; these may be performed at any time between signing informed consent and first dose of RPC1063 in RPC01-3001. The RPC01-1001 End of Study assessments and the RPC01-3001 Baseline procedures may be performed on the same day.

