12.2.1. Clinical Laboratory Parameters and Abnormal Laboratory Test Results

Hematology

Starting with the Month 3 visit (ie, excluding the Baseline visit), complete hematology laboratory values will be available to the Investigator. Reductions in ALC levels is a known pharmacodynamic effect of RPC1063. If any of the following results are observed, the Investigator will be notified and asked to repeat the laboratory tests within approximately 7 days:

- Absolute lymphocyte count [ALC] < 200 cells/ μ L
- Absolute neutrophil count [ANC] < 1000 cells/ μ L
- Total WBC > 20,000 cells/ μ L

If the ANC is confirmed < 1000 cells/ μ L, the Investigator will be requested to closely monitor for risk of serious infection and institute appropriate follow-up at his or her discretion.

If ALC is confirmed < 200 cells/ μ L, the Investigator will temporarily discontinue treatment and then consult the Medical Monitor. Laboratory testing will be repeated weekly until ALC is > 500 cells/ μ L. When ALC has returned to > 500 cells/ μ L, treatment may be reinitiated at the Investigator's discretion. (See Section 9.3.1 for instructions on resuming treatment after missing doses.)

For patients who permanently discontinue treatment or complete the trial, central laboratory testing of ALC will continue every 14 days (\pm 3 days) after discontinuation of RPC1063 or the End of Treatment/Early Termination Visit until ALC is above the lower limit of normal.

If an ALC Follow-up Visit is needed within the window of the 90-Day Safety Follow-up Visit, the patient should only return for the 90-Day Safety Follow-up Visit and ALC should be collected at that visit.

If the patient has started a lymphocyte-depleting treatment during the Safety Follow-up period, ALC should only be determined at the 90-Day Safety Follow-up Visit. The Medical Monitor should be consulted if the ALC is not $>$ LLN by the Day 90 Safety Follow-up Visit for subjects not started on lymphocyte-depleting disease modifying therapies (DMTs), and ALC visits should continue every 14 days (\pm 3 days) until the Investigator is notified to discontinue.

Liver Function Tests

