- It disappears or decreased on cessation or reduction in dose. There are exceptions when an AE does not disappear upon discontinuation of the drug (eg, bone marrow depression, fixed drug eruptions, tardive dyskinesia, etc.)
- It follows a known pattern of response to the suspected drug
- It reappears or worsens if the drug is re-administered

All efforts should be made to classify the AE according to the above categories.

After initiation of investigational drug, all AEs, regardless of relationship to investigational drug, will be recorded until the patient completes his or her last trial visit.

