12.4.3 COVID-19 Pandemic

The global coronavirus disease 2019 (COVID-19) pandemic has been identified as a potential risk to clinical trial subjects in general and may particularly affect individuals with underlying chronic diseases on immunomodulatory therapies. It is not known whether taking ozanimod increases the risk of SARS-CoV-2 infection, or the duration or severity of COVID-19.

Evaluation and management of SARS-CoV-2 infections arising during the course of the trial are left to the discretion and expertise of the investigator. For subjects who exhibit symptoms consistent with SARS-CoV-2, testing for SARS-CoV-2 to inform decisions and clinical care during the study should follow local standard practice. The sponsor also suggests the investigator to refer to the Multiple Sclerosis International Federation (MSIF) guidelines per DMC recommendation, and to consult the Medical Monitor as needed.

Each study visit will include an assessment for AEs including SARS-CoV-2 and other infections. In order to facilitate reporting of SARS-CoV-2 events that occur during the study, all AEs and SAEs related to SARS CoV-2 should be reported from the time of consent until the final study Visit.

Procedures related to COVID-19 identification (eg, MERS-CoV test, SARS-CoV-2 antibody test, SARS-CoV-2 ELISA test), and treatment (eg, intubation, dialysis) must be reported in the appropriate eCRF.

Non-live COVID-19 vaccination is considered a simple concomitant medication within the study. However, the safety and efficacy of non-live vaccines (including non-live COVID-19 vaccines) in patients receiving ozanimod is unknown. Ozanimod treatment may cause vaccines to be less effective. If the assessment of the Investigator suggests the vaccine to be beneficial, it must be a non-live, replication incompetent vaccine, and be approved or authorized (ie, Emergency Use Authorization [FDA] or equivalent) by national health authorities.

Administration of vaccinations must be reported along with dosage information, dates of administration and vaccine name/trade name in the appropriate eCRF. A separate logline should be entered for each vaccine administered with the dose number following the vaccine name/trade name.

12.4.4 Monitoring of Patients with Adverse Events, Serious Adverse Events, and Adverse Events of Special Interest

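### Table 2 schedules no adverse-event check at ALC Follow-up Visits although the text requires one at every visit; after Day 90 this can leave events in unrecovered patients uncollected

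*Combined protocol and SAP*

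**What the plan says.** Three places in the text set a rule for collecting adverse events.

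- Section 12.3.1: "Investigators will ask the patient at each visit if they have experienced any untoward occurrence since the last trial visit". The same section monitors events "throughout the duration of their participation in the trial, including the 90-Day Safety Follow-up Visit".
- Section 12.3.4: after the first dose all AEs, related or not, "will be recorded until the patient completes his or her last trial visit".
- Section 12.4.3: "Each study visit will include an assessment for AEs including SARS-CoV-2 and other infections".

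Section 12.4 adds SAE reporting from consent to the last visit, and also for 90 days after the last dose.

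Table 2 has eight visit columns. The ALC Follow-up Visit ("every 14 days after last dose") is the sixth. The adverse-event row ("AEs/SAEs X X X X X X X") carries seven marks, and so does the medication row ("Prior/concomitant therapy X X X X X X X"). In both rows the empty cell is the ALC Follow-up Visit, where only clinical laboratory tests are marked. Footnote c to that column deals with ALC testing alone.

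Section 12.2.1 lets these visits run beyond Day 90. If the ALC is still not above the lower limit of normal and the patient has not started a lymphocyte-depleting therapy, "ALC visits should continue every 14 days" until the site is told to stop. No end date is given.

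**The concern.** A site cannot satisfy both Table 2 and the text. Section 7.1 lists the ALC Follow-up Visits among the scheduled trial visits, and Section 8.2 encourages patients to attend them so that safety data can be gathered. They therefore fall under the each-visit rules of Sections 12.3.1 and 12.4.3. Yet the schedule that site staff work from asks only for a blood sample. With about 275 sites, practice can differ.

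The primary objective is long-term safety, and serious and opportunistic infections are adverse events of special interest (Section 12.4.2). Patients who still have a low lymphocyte count after stopping are a group in whom such infections are of direct interest. Section 12.2.2 itself points to the long half-lives of the active metabolites and provides for patients with prolonged ALC recovery. The treatment-emergent definition in Section 13.3.2 has no end date, so a late infection enters the safety tables if it is recorded. Whether it is recorded would depend on which part of the protocol the site follows.

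**Working it through.** There is no sample size or test to reproduce, and the plan gives no figure for this point. The check lays the visit calendar out against the scheduled adverse-event checks.

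**Inputs**
- ALC visits every 14 days after the last dose, ± 3 days (Table 2).
- Safety visits with an AE and medication check: Day 28 ± 7, so Days 21 to 35; Day 90 ± 10, so Days 80 to 100 (Table 2).
- Withdrawal battery with an AE and medication check at Days 1, 4, 7, 14, 21 and 90, until the sponsor ends it (Table 3, Section 7.1).
- An ALC visit falling in the Day 90 window is merged into the Day 90 visit (Section 12.2.1; Table 2, footnote c).

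**Calendar on nominal days**

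| ALC day | What is scheduled |
|---|---|
| 14 | AE check through Table 3, while that battery runs |
| 28 | AE check at the Day 28 visit |
| 42, 56, 70 | ALC only |
| 84, 98 | Inside Days 80 to 100, merged into the Day 90 visit, AE check |
| 112, 126, 140 and onward | ALC only |

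**Day 28 to Day 90.** The interval without a scheduled AE check is 90 − 28 = 62 days. With visit windows it runs from 80 − 35 = 45 to 100 − 21 = 79 days. Three nominal ALC visits fall inside it. The Day 90 visit asks about everything since the previous visit. If no clinic visit is possible, footnote m still requires a telephone contact that records AEs and medications.

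**After Day 90.** The first nominal ALC-only visit is Day 112. No later visit in Table 2 or Table 3 carries an AE check, and the Unscheduled Relapse Visit is provided only before the 90-Day visit. As an illustration, assume a patient is followed to nominal Day 182. That patient makes six ALC-only visits (112, 126, 140, 154, 168, 182) and has 182 − 90 = 92 days with no scheduled AE question.

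**Concomitant medication.** The three AE rules do not cover medication. Section 9.5 requires treatments to be documented through the Day 90 visit, and Section 12.1.10 says use is monitored throughout the trial. The blank medication cell is therefore an omission after Day 90, not a contradiction of Sections 12.3.1, 12.3.4 and 12.4.3.

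**The case against.** The strongest reply is that an empty table cell does not cancel the text. Sections 12.3.1, 12.3.4 and 12.4.3 still require AEs to be collected, Section 12.4 still requires SAEs through the last visit, and an unrecovered ALC at Day 90 prompts consultation with the Medical Monitor. This stands in part. A reader might infer from Table 2 that infections in these patients are missed. The documents support only a risk of that, at sites that follow the table.

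Three further inferences are tempting and do not hold.

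- That recall between Day 28 and Day 90 is unusually long. Even the 79-day maximum is below the routine 91-day interval on treatment, and well below the six-month interval used after the third annual visit.
- That late ALC values cannot be interpreted without medication data. Lymphocyte-depleting agents are prohibited through Day 28 (Section 9.5.1). A patient who starts one in the safety follow-up period leaves the 14-day series and has ALC measured only at Day 90, where medications are collected. What remains open is a depleting drug started after Day 90.
- That Section 12.4 gives two conflicting SAE end points. Its wording makes the 90-day rule additional to reporting through the last visit. What is unclear is only whether an ALC visit after Day 90 is the last visit.

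The reply does not remove the mismatch itself, and it does not supply a scheduled AE check after Day 90.

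**Conclusion.** The inconsistency is real: Table 2 omits an AE/SAE check that three sections require. Up to Day 90 the consequence is limited to later collection. From nominal Day 112 onward, patients whose ALC has not recovered attend every 14 days with no scheduled AE/SAE or medication check and no later scheduled visit at which events could be recovered, so infections may be missed.

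The size in patients cannot be given. The documents do not state how many are expected to be unrecovered at Day 90, or for how long. Patients who start commercial ozanimod within 14 days of stopping are excused from the safety follow-up visits (Section 7.1), so the point mainly concerns the others. The calendar rests on nominal visit days and on the rule that ALC visits in the Day 90 window are merged. If the sponsor has already ended the withdrawal battery, the Day 14 ALC visit also has no AE check, but Day 28 then covers that interval.

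**What to change.** Reconcile Table 2 with Sections 12.3.1, 12.3.4, 12.4 and 12.4.3:

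1. Mark AEs/SAEs in the ALC Follow-up Visit column of Table 2.
2. Mark prior/concomitant therapy in the same column, to close the omission after Day 90.
3. State in Sections 12.3.1 and 12.4 that an ALC visit held after Day 90 counts as the last visit for AE and SAE collection.

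The cost is a table correction, two clarifying sentences, and a few questions at blood-draw visits that already take place. No visit or test is added. Tabulating post-Day-90 events separately would be a reporting preference and is not needed to resolve the point.

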12.3.2 Definition of Serious Adverse Events

An SAE (experience) or reaction is any untoward medical occurrence that at any dose (ICH E2A, II.B):

- Results in death
- Is life-threatening

NOTE: The term "life-threatening" in the definition of "serious" refers to an event in which the patient was at risk of death at the time of the event; it does not refer to an event which hypothetically might have caused death if it were more severe.

- Requires inpatient hospitalization or prolongation of existing hospitalization

- Results in persistent or significant disability/incapacity, or
- Is a congenital abnormality/birth defect

Medical and scientific judgment should be exercised in deciding whether expedited reporting is appropriate in other situations, such as important medical events that may not be immediately life-threatening or result in death or hospitalization but jeopardize the patient or may require intervention to prevent one of the other outcomes listed in the definition above. *These should also usually be considered serious.*

Examples of such events are intensive treatment in an emergency room or at home for allergic bronchospasm; blood dyscrasias or convulsions that do not result in hospitalization; or development of drug dependency or drug abuse.

In case of a fatality, the cause of death is considered as the SAE, and the death is considered as its OUTCOME.

Uncomplicated cases of relapse and MS disease progression requiring hospitalization or otherwise meeting the above serious criteria do not need to be reported as SAEs, unless there are other diagnoses or complications which meet serious criteria.

12.3.3 Assessment of Adverse Event Severity

The severity of the AE will be characterized as “mild, moderate, or severe” according to the following definitions:

- Mild events are usually transient and do not interfere with the patient’s daily activities.
- Moderate events introduce a low level of inconvenience or concern to the patient and may interfere with daily activities.
- Severe events are incapacitating and interrupt the patient’s usual daily activity.

12.3.4 Assessment of Adverse Event Relationship to Investigational Drug

The causal relationship between RPC1063 and the AE has to be characterized as unrelated, unlikely, possible, probable, or related. This medical assessment should be made as soon as feasible when reporting an SAE.

The Investigator is requested to assess the relationship of any AEs to treatment using the following definitions:

Unrelated: those AEs which are clearly and incontrovertibly due to extraneous causes (concurrent drugs, environment etc.) and do not meet the criteria for drug relationship listed under Unlikely, Possible, Probable or Related.

Unlikely: An AE may be considered unlikely if it includes at least the first two features:

- It does not follow a reasonable temporal sequence from administration of the drug
- It could readily have been produced by the patient’s clinical state, environmental or toxic factors, or other modes of therapy administered to the patient

- It does not follow a known pattern to the suspected drug
- It does not reappear or worsen when the drug is re-administered

Possible: An AE may be considered possible if it includes at least the first two features:

- It follows a reasonable temporal sequence from administration of the drug
- It could readily have been produced by the patient's clinical state, environment or toxic factors, or other modes of therapy administered to the patient
- It follows a known response pattern to the suspected drug

Probable: An AE may be considered probable if it includes at least the first three features:

- It follows a reasonable temporal sequence from administration of the drug
- It could not be reasonably explained by the known characteristics of the patient's clinical state, environmental or toxic factors or other modes of therapy administered to the patient
- It disappears or decreased on cessation or reduction in dose. There are exceptions when an AE does not disappear upon discontinuation of the drug (eg, bone marrow depression, fixed drug eruptions, tardive dyskinesia, etc.)
- It follows a known pattern of response to the suspected drug

Related: an AE may be considered related if it includes all of the following features:

- It follows a reasonable temporal sequence from administration of the drug
- It could not be reasonably explained by the known characteristics of the patient's clinical state, environmental or toxic factors or other modes of therapy administered to the patient
- It disappears or decreased on cessation or reduction in dose. There are exceptions when an AE does not disappear upon discontinuation of the drug (eg, bone marrow depression, fixed drug eruptions, tardive dyskinesia, etc.)
- It follows a known pattern of response to the suspected drug
- It reappears or worsens if the drug is re-administered

All efforts should be made to classify the AE according to the above categories.

After initiation of investigational drug, all AEs, regardless of relationship to investigational drug, will be recorded until the patient completes his or her last trial visit.

12.4 Reporting of Serious Adverse Events

Full details of the procedures to be adopted will be documented in a safety management plan approved by responsible parties, in brief:

The Investigator will report any SAE that occurs to any patient from the time written informed consent is signed through the last visit. If an SAE occurs after informed consent and is resolved

before the first dose of investigational drug in RPC01-3001, the event will be captured in the parent trial only. If the SAE is ongoing at the time of the first dose in RPC01-3001, it will be transcribed into the eCRF for RPC01-3001. All SAEs that occur within 90 days of the last dose of treatment with the investigational drug, whether or not considered related to the investigational product, must also be reported. Any SAE that is ongoing when the patient completes the trial or withdraws from the trial will be followed by the Investigator until the event has resolved, stabilized, or returned to baseline status. The following are not generally considered valid SAEs: hospitalizations or procedures planned prior to signing the informed consent form (ICF), hospitalizations that are <24 hours, admission for elective procedures that are not a result of a worsening condition, or admissions for procedures required by protocol.

An electronic form must be completed in the eCRF or a written SAE report must be sent within 24 hours from the time the trial site personnel first learned of the event. For Safety contact information, please refer to the Celgene General Guidelines for SAE Recording and Reporting.

